6.1.1.4. Rilpivirine Injectable Suspension (RPV LA)

RPV LA (also named JNJ-16150108-AAA), 300 mg/mL Extended Release Suspension for Injection (G001), is provided by Janssen Research & Development, LLC, a division of Janssen Pharmaceuticals, as a sterile white suspension containing 300 mg/mL of RPV as the free base. The route of administration is by intramuscular (IM) injection. RPV LA is packaged in a single use 4 mL glass vial with a 13 mm grey stopper and aluminum seal. Each vial contains a nominal fill of 2.0 mL (600 mg) or 3.0 mL (900 mg), and does not require dilution prior to administration. RPV LA injectable suspension is to be stored according to product labeling. RPV LA should also be protected from light.

RPV LA is composed of RPV free base, poloxamer 338, sodium dihydrogen phosphate monohydrate, citric acid monohydrate, glucose monohydrate, sodium hydroxide, water for injection.

6.2. Treatment Assignment

Informed consent must be obtained prior to any study procedures, including Screening visit activities. Participants will be assigned to study treatment in accordance with the randomization schedule. The randomization schedule, including stratification, will be generated using the GSK validated randomization software RANDALL NG. The

randomization schedule is comprised of a series of blocks, with equal treatment allocation within each block, which are shared across centers via central randomization. Given the open-label study design, central randomization was used to eliminate selection bias due to foreknowledge of randomized treatment. With central randomization, knowledge at a site of the randomized treatment group for previous subjects does not predict which treatment group will be assigned to the next randomized subject.

Randomization and study treatment assignment will be facilitated by the interactive response technology (IRT) through the central Randomization and Medication Ordering System Next Generation (RAMOS NG).

Following confirmation of fulfillment of study entry criteria, study site personnel will be required to register participants using RAMOS NG for assignment of a unique identifier (designating the participant's randomization code and treatment sequence assignment) for each participant participating in the study. A unique treatment number will be assigned for each participant participating in the study. Participants will be randomized in a 1:1 ratio to CAB LA + RPV LA Q4W or to CAB LA + RPV LA Q8W in accordance with the computer generated randomization schedule.

Participants who successfully complete 100 weeks of treatment and have a viral load <50 c/ml at Week 96 (or upon retest by Week 100) will be given the opportunity to enter the Extension Phase in which they will continue to receive their CAB LA + RPV LA regimen. In addition, RAMOS NG will facilitate the initial supply and subsequent resupply of IP to study sites.

6.3. Dosage and Administration

Participants will be randomly assigned to receive treatment with CAB LA + RPV LA either Q4W or Q8W. Patients transitioning from oral standard of care therapy will initiate their randomized treatment regimen with Oral CAB 30 mg + RPV 25 mg once daily for 4 to 5 weeks during the Oral Phase, followed by CAB LA + RPV LA IM injections initiating at Week 4b. Patients transitioning from the ATLAS study and on CAB LA + RPV LA Q4W treatment will be randomized at Day 1 to either continue Q4W administration or transition to Q8W administration of CAB LA + RPV LA. Regardless of treatment arm assignment, the investigator should instruct all participants on the importance of treatment adherence. This study has an open-label design. Dosing is outlined in [Table 7 Figure 8](#) below.

Table 7 Dosage and Administration

Maintenance Phase and Extension Phase (Day 1 to End of Study⁺)	
Q4W Arm - Transitioning from SOC	
Oral Lead-In	
Day 1 to Week 4b (2 tablets once daily)	
 • Take 1 tablet CAB 30 mg once daily. • Take 1 tablet RPV 25 mg once daily. 
Should be taken together once daily at approximately the same time each day, with a meal.

First Injections (Loading Dose) – Week 4b	
Week 4b (two 3mL injections once)	
 • Receive last dose of oral CAB + RPV regimen • Receive CAB LA 600 mg given as 1 X 3 mL IM injection • Receive RPV LA 900 mg given as 1 X 3 mL IM injection
Maintenance Injections – every 4 Weeks (Q4W) following Week 4b	
Week 8 to End of Study ⁺ (two 2 mL injections every 4 weeks)	
 • Receive CAB LA 400 mg given as 1 X 2 mL IM injection • Receive RPV LA 600 mg given as 1 X 2 mL IM injection
Q8W Arm-Transitioning from SOC	
Oral Lead-In	
Day 1 to Week 4b (2 tablets once daily)	
 • Take 1 tablet CAB 30 mg once daily. • Take 1 tablet RPV 25 mg once daily. 
Should be taken together once daily at approximately the same time each day, with a meal.

First Injections (Loading Doses) – Week 4b	
Week 4b (two 3 mL injections once)	
 • Receive last dose of oral CAB + RPV regimen • Receive CAB LA 600 mg given as 1 X 3 mL IM injection • Receive RPV LA 900 mg given as 1 X 3 mL IM injection

Maintenance Injections – every 8 Weeks (Q8W) following Week 8	
Week 8 to End of Study+ (two 3mL injections every 8 weeks)	
 • Receive CAB LA 600 mg given as 1 X 3 mL IM injection • Receive RPV LA 900 mg given as 1 X 3 mL IM injection
Q4W Arm – Continuing Q4W injections from ATLAS	
Day 1 to End of Study+ (two 2 mL injections every 4 weeks)	
 • Receive CAB LA 400 mg given as 1 X 2 mL IM injection • Receive RPV LA 600 mg given as 1 X 2 mL IM injection
Q8W Arm- Transitioning from ATLAS Q4W	
Day 1 to End of Study+ (two 3 mL injections every 8 weeks)	
 • Receive CAB LA 600 mg given as 1 X 3 mL IM injection • Receive RPV LA 900 mg given as 1 X 3 mL IM injection

+Until locally approved and commercially available, the participant no longer derives clinical benefit, the participant meets a protocol-defined reason for discontinuation or until development of CAB LA or RPV LA is terminated Participants will be given an option to continue their randomized Q4W or Q8W CAB LA + RPV LA regimen (or complete trial participation) at Week 100. If the participant decides not to continue participation in the study, any arrangements for off-study ART should be made in advance of the Week 100 visit. ^See Section 6.6.1 for Dosing Considerations for CAB LA + RPV LA
	

6.4. Blinding

This will be an open-label study and therefore no blinding is required. No summaries of the study data according to actual randomized treatment groups will be available to sponsor staff prior to the planned Week 24 preliminary analysis. The Week 24 results will be restricted to only those study team members and GSK/ViiV Healthcare senior management who need to be involved in the analysis and interpretation of the results for reporting to regulatory authorities. Public presentation of the Week 24 analysis will not be done prior to Week 48 analysis complete.

6.5. Packaging and Labeling

The contents of the label will be in accordance with all applicable regulatory requirements.

6.6. Preparation/Handling/Storage/Accountability

- The investigator or designee must confirm appropriate temperature conditions have been maintained during transit for all study treatment received and any discrepancies are reported and resolved before use of the study treatment.
- Only participants enrolled in the study may receive study treatment and only authorized site staff may supply or administer study treatment. All study treatments

must be stored in a secure, environmentally controlled, and monitored (manual or automated) area in accordance with the labeled storage conditions with access limited to the investigator and authorized site staff.

- In accordance with local regulatory requirements, the investigator, institution, or the head of the medical institution (where applicable) is responsible for study treatment accountability, reconciliation, and record maintenance (i.e. receipt, reconciliation and final disposition records). The amount of IP dispensed and/or administered to study participants, the amount returned by study participants, and the amount received from and returned to GSK must be documented.
- Further guidance and information for the final disposition of unused study treatment are provided in the Study Reference Manual.
- Under normal conditions of handling and administration, study treatment is not expected to pose significant safety risks to site staff. Take adequate precautions to avoid direct eye or skin contact and the generation of aerosols or mists. In the case of unintentional occupational exposure notify the monitor, Medical Monitor and/or GSK study contact.
- A Material Safety Data Sheet (MSDS)/equivalent document describing occupational hazards and recommended handling precautions either will be provided to the investigator, where this is required by local laws, or is available upon request from GSK.
- Product accountability records must be maintained throughout the course of the study.

IP accountability will be evaluated using pill counts of unused IP for patients receiving oral treatment (oral CAB, oral RPV). This assessment will be conducted, when the participant completes oral CAB and RPV lead-in treatment in the Maintenance or Extension Phase, or any withdrawal that occurs during an oral treatment phase.

IP accountability for participants receiving CAB LA + RPV LA will be performed at the 'vial' level (e.g., correct number of vials were used for each injection). There may be a small amount of solution remaining in the vial which does not require quantification. Used vials may be discarded at the site once accountability is complete.

6.6.1. Dosing Considerations for CAB LA + RPV LA

Vials of CAB LA and RPV LA are each supplied as a suspension and need no further dilution or reconstitution. Since RPV LA requires refrigeration, sites should allow the vial to come to approximately room temperature prior to injecting. The vials should be gently inverted a few times to re-suspend sediments and allow bubbles to subside, and then use a syringe to withdraw the required volume of suspension for IM injection.

All injections must be given intramuscularly in the gluteus medius. Sites may use their discretion as to where in the gluteus muscle each injection is given according to individual participant circumstance. If possible, injections should be spaced approximately 2 cm from one another, from the site of any previous injection or any injection site reaction. The time and location of injection will be captured in the eCRF.

IM injections should be administered at a 90 degree angle into the gluteus medius muscle using a needle of appropriate gauge and length (In most participants, a 1.5” 23 gauge needle for CAB LA and a 1.5” 23 gauge needle for RPV LA is recommended). The needle should be long enough to reach the muscle mass and prevent study drug from seeping into subcutaneous tissue, but not so long as to involve underlying nerves, blood vessels, or bone. Variable needle lengths and/or needles with different gauge (CAB LA: 21 to 25 gauge; RPV LA: 21 to 23 gauge) are permitted if needed to accommodate individual body types. Longer needle lengths may be required for participants with higher body mass indexes (BMIs, example > 30), to ensure that injections are administered intramuscularly as opposed to subcutaneously. BMI, needle gauge and length used will be collected in the eCRF. Additional details of the injection device used by sites for IM administration including, but not limited to functional performance, may also be collected within the eCRF.

At the Week 4b visit, participants transitioning from oral SOC should be dosed with the IM regimen within 2 hours of taking the last oral regimen dose where possible.

Should IM maladministration be suspected at any time (e.g., suspected under or overdose or inadvertent IV dosing), the investigator may consider requesting the participant stay onsite for approximately 2-3 hours post dose for safety monitoring and notifying the Medical Monitor. An ECG or any other supportive testing may be obtained at the discretion of the investigator. Additionally, a PK sample may be drawn approximately 2 hours post dosing for future evaluation of CAB and RPV plasma concentrations.

Additional dosing instructions and considerations can be found in the SPM.

6.7. Compliance with Study Treatment Administration

When participants are dosed at the site, they will receive study treatment directly from the investigator or designee, under medical supervision. The date and time of each dose administered in the clinic will be recorded in the participant’s eCRF. The dose of study treatment and study participant identification will be confirmed at the time of dosing by a member of the study site staff other than the person administering the study treatment.

When participants self-administer oral study treatments at home, compliance with CAB + RPV dosing will be assessed through querying the participant during the site visits and documented in the source documents and CRF. IP accountability will be evaluated using pill counts of unused IP (CAB and RPV tablets). This assessment will be conducted each time the participant receives a new (refill) supply of oral study medication, completes the oral lead-in or any oral bridging phase. A record of the number of CAB and RPV tablets dispensed to and taken by each participant must be maintained and reconciled with study treatment and compliance records. Treatment start and stop dates will also be recorded in the eCRF.

Due to the long acting nature of the CAB LA and RPV LA it will be imperative that the participant is compliant with dosing instructions. As part of the screening and participant selection process, it is imperative that Investigators discuss with potential participants the long-term commitments for the trial, and the importance of adhering to treatment regimens. Sites are to have plans in place for adherence counselling for both treatment arms of the study for the duration of the study including the LTFU Phase. In addition, Investigators must have plans in place to perform visit reminders, utilizing patient trackers provided by the study team as needed, and to verify the participant's contact information at each visit. Investigators should contact patients directly in the event that a participant misses any scheduled visit.

6.8. Protocol Permitted Substitutions

6.8.1. Oral Bridging

In exceptional circumstances, to address pre-planned missed CAB LA + RPV LA dosing visits, in consultation with the medical monitor, Investigators may provide daily oral CAB 30 mg and RPV 25 mg as a short-term "bridging" strategy for participants who have begun CAB LA + RPV LA. In certain circumstances (e.g., prior to steady state dosing and following a >4 week oral bridge) repeating the loading doses of CAB IM and RPV IM may be required. Should a participant require "oral bridging", sites must contact the study Medical Monitor for guidance with treatment and dosing strategies prior to a missed CAB LA + RPV LA dose.

6.9. Interruption of Study Treatment and Visit/Dosing Windows

IP may be interrupted at the discretion of the Investigator in the event of an AE, according to the severity of the AE.

If one or more antiretroviral medications is held due to toxicity or adverse events, all antiretroviral medications must be held to reduce the risk of development of resistance taking into account both the length of the planned interruption and the pharmacokinetic half-life of each antiretroviral of the regimen, in a way to minimize the risk of development of resistance.

It is important to note that keeping to the participant's visit schedule is a very important component to the study.

Note: All decisions regarding dose interruption / resumption must be discussed with the medical monitor in advance.

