- Participants who are not eligible to continue into the Maintenance Phase.
- Participants who are not eligible, or do not wish to continue on to the Extension Phase.
- Virologic withdrawal criteria as specified in Section 5.5.4 are met;
- Participant requires substitution of ART;
- Participant requires substitution or dose reduction of CAB LA or RPV LA (oral bridging supply and potential for a second loading dose may be permissible following discussion with the Medical Monitor).
- Liver toxicity where stopping criteria are met and no compelling alternate cause is identified (see Section 5.5.1);
- Renal toxicity are met and no compelling alternate cause is identified;
- QT interval (QTc) interval >550 msec from three or more tracings separated by at least 5 minutes and considered causally related to IP.
- Grade 4 clinical AE considered causally related to study drug;
- Participant has a Grade 3 or higher rash or Grade 2 rash with evidence of systemic involvement and no compelling alternative cause is identified
- Pregnancy (intrauterine), regardless of termination status of pregnancy.
- Participant withdrew consent

Efficacy data for participants withdrawing from the study will be considered evaluable up to the point at which they are withdrawn using the same criteria for evaluability as for participants who complete the study.

Safety data for all participants who receive any amount of study drug, including participants who withdraw from the study, will be included in evaluations of safety.

All data from the Withdrawal visit will be recorded, as they comprise an essential evaluation that should be done prior to discharging any participant from the study.

The following actions must be taken in relation to a participant who fails to attend the clinic for a required study visit:

- a. The site must attempt to contact the participant and re-schedule the missed visit as soon as possible.

- b. The site must counsel the participant on the importance of maintaining the assigned visit schedule and ascertain whether or not the participant wishes to and/or should continue in the study.

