6.9.1. IM Dosing

Participants receiving CAB LA and/or RPV LA are anticipated to be at risk for development of virologic resistance if ART is interrupted. The time period during which participants are at risk for development of virologic resistance may be determined by the period between when drug levels fall below therapeutic values and when they fall below levels which exert selective pressure on HIV. This time period will vary by ART agent and is dependent upon effective concentration, inhibitory concentration, and half-life.

Plasma concentrations of both LA drugs may be measurable for more than one year following IM injections. Any interruption in IM dosing should be discussed with the Medical Monitor. Investigators should ensure that the participant initiates alternative highly active ART to minimize the risk of developing resistance as concentrations of CAB and RPV decline over time.

IM dosing is expected to occur during the week in which the participant's projected visit falls (as according to the date of the first injection). The first injections for participants from ATLAS on CAB LA + RPV LA Q4W will occur at Day 1. The first injections for participants transitioning from oral SOC are administered at Week 4b (can be performed as soon as lab results from Week 4a become available and should be performed where possible within 2 weeks of visit 4a), and the second injections are given at Week 8. Between the Week 4a and 4b visits, participants must continue daily treatment with oral CAB and RPV tablets.

Since the first injection visit (Day 1 or 4b) will determine the future injection visit schedule for participants, planning for the first injection visit date (within allowed visit windows) should take into consideration the availability of the participants to adhere to future visit windows (planned vacations, business trips, *etc.*).

CAB LA + RPV LA dosing for participants transitioning from SOC treatment is as follows:

All injections should be planned as single injections per drug.

6.9.1.1. IM injections every 4 weeks (Q4W):

Week 4b only - CAB LA 600 mg + RPV LA 900 mg, each given as 1 X 3 mL IM injection

Week 8 and Q4W thereafter - CAB LA 400 mg IM + RPV LA 600 mg IM every 4 weeks for 100 weeks, each given as 1 X 2 mL IM injection

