7.4.4.1. Treatment Interruption Due to an Adverse Event

IP may be interrupted at the discretion of the investigator and according to the severity of the AE. If one or more ART medication is held due to toxicity or AEs, all ART medications should be held to reduce the risk of development of resistance taking into account the length of the planned interruptions and the PK half-life of each ART of the regimen, in order to minimize the risk of development of resistance.

No toxicity-related dose reductions of IP will be allowed. IP should be restarted as soon as medically appropriate; in general, for oral dosing, this should be no longer than 14 days after discontinuation (unless Grade 3 or 4 toxicities persist). Any interruption in therapy during the Maintenance Phase, oral dosing, of greater than 7 consecutive days must be discussed with and agreed by the Medical Monitor prior to resumption of therapy. The Medical Monitor must be contacted upon becoming aware of resumption in therapy, if therapy was resumed without prior approval (Section 6.9). **IM dosing is expected to occur during the week in which the participant’s projected visit falls (as according to the first injection visit). An additional (+ or -) 7 day window, from the**

projected visit date, is allowable for IM dosing but not preferred. Any interruption outside of this guidance **MUST** be discussed with the Medical Monitor prior to reinitiating IM IP (see Section 6.9.1).

Guidance is provided below on general participant management and IP interruptions based on the severity of the AE. Information regarding permitted substitutions \ is provided in Section 6.8. All changes in the IP regimen must be accurately recorded in the participant's eCRF.

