7.4.4.3. Grade 3 Toxicity/Adverse Event

Participants who develop a Grade 3 AE or toxicity should be managed as follows:

- If the Investigator has compelling evidence that the Grade 3 AE or toxicity has not been caused by IP, dosing may continue after discussion with the Medical Monitor.
- Participants who develop a Grade 3 AE or toxicity, which the Investigator considers related or possibly related to the IP, should have the IP withheld and be rechecked each week until the AE returns to Grade 2. Once the AE is Grade \leq 2, IP may be re-started.
- Should the same Grade 3 AE recur within 28 days in the same participant, the IP should be permanently discontinued and the participant withdrawn from study.
- Participants experiencing Grade 3 AEs requiring permanent discontinuation of IP should be followed weekly until resolution of the AE and to have withdrawal study evaluations completed. A follow-up visit should be performed 4 weeks after the last dose of IP. Any participant receiving at least one dose of CAB LA and /or RPV LA who discontinue IP / Withdraw will initiate treatment with HAART and enter the LTFU Phase for 52 weeks of follow up.

- Participants with Grade 3 asymptomatic laboratory abnormalities should be investigated for all potential non-drug related causes, and, following discussion with the Medical Monitor, may continue IP if the Investigator has compelling evidence that the toxicity is not related to IP, with the exception of liver chemistry stopping criteria (See Section 7.4.5.1). Isolated Grade 3 lipid abnormalities do not require withdrawal of IP.

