9.3. Key Elements of Analysis Plan

9.3.1. Primary Analyses

For the primary efficacy analysis, virologic outcome for each participant in the Intent-to-Treat Exposed population will be calculated according to the FDA's Snapshot algorithm. The primary analysis at Week 48 will take place after the last participant has had their Week 48 viral load assessed, including a retest if required.

As defined by the Snapshot algorithm, HIV-RNA ≥ 50 copies/mL is determined by the last available HIV-1 RNA measurement while the participant is on treatment within the analysis visit window of interest. In addition, participants without evaluable HIV-RNA data for the visit of interest and who discontinue from the maintenance phase for reasons not related to adverse event with HIV-1 RNA result at the time of discontinuation ≥ 50 copies/mL or who change study treatment not permitted per protocol before the analysis window are classified as having HIV-RNA ≥ 50 copies/mL.

For the primary efficacy analysis, the adjusted difference between the randomized arms for the proportion of participants with HIV-1 RNA ≥ 50 c/mL at Week 48 (according to the FDA snapshot algorithm) and its confidence interval will be calculated according to a stratified analysis with Cochran-Mantel Haenszel (CMH) weights. This analysis will adjust for the randomization strata (rederived for analysis to correct for stratification errors) according to prior exposure to CAB + RPV (0 weeks, 1-24 weeks, >24 weeks).

The CMH estimate of the common difference in rates across strata will be calculated as the weighted average of the strata-specific estimates of the difference in proportion between the two arms as follows:

- If n_k is the number of Q8W treated participants, m_k is the number of Q4W arm treated participants, and $N_k = n_k + m_k$ is the total number of participants in the k th stratum, then the CMH estimate is given by

$$\hat{d}_{cmh} = \frac{\sum W_k \hat{d}_k}{\sum W_k}$$

where

$$W_k = \frac{n_k m_k}{N_k}$$

are CMH weights and \hat{d}_k are estimates of the differences in proportions between the two treatment arms, $f_{Q8W} - f_{Q4W}$, for the k th stratum.

The corresponding two-sided 95% CI will be calculated as:

$$\hat{d}_{cmh} \pm 1.96 \times \sqrt{\hat{\text{var}}(\hat{d}_{cmh})}$$

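### For an injection held for toxicity, Sections 6.9 and 7.4.4.1 conflict with Section 6.9.1 on whether other ART is started, and the Snapshot status of any ART so started is left ambiguous

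*Protocol*

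**What the plan says.** **Hold rule.** Protocol Section 6.9, the parent of both the intramuscular (6.9.1) and oral (6.9.2) subsections: "If one or more antiretroviral medications is held due to toxicity or adverse events, all antiretroviral medications must be held to reduce the risk". Section 7.4.4.1, on interruption for an adverse event: "all ART medications should be held to reduce the risk of development of resistance".

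**Alternative-ART rule.** Section 6.9.1: "Any interruption in IM dosing should be discussed with the Medical Monitor". The next sentence reads: "Investigators should ensure that the participant initiates alternative highly active ART to minimize the risk of developing resistance".

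**Temporary holds are planned for.** For a Grade 3 event considered related or possibly related, Section 7.4.4.3 says participants "should have the IP withheld and be rechecked each week until the AE returns to Grade 2", after which study drug may be restarted.

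**Rules on other ART.** Section 5.5 lists "Participant requires substitution of ART" among the reasons for mandatory discontinuation of study treatment. Section 5.5.5 permits no ART change before protocol-defined virologic failure outside the planned regimens. Section 6.13.2 prohibits antiretrovirals that the protocol does not otherwise specify.

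**Endpoint rule.** Under Section 9.3.1, participants without evaluable data "who change study treatment not permitted per protocol before the analysis window are classified as having HIV-RNA" at or above 50 c/mL. A separate limb of the same sentence gives that outcome to participants who discontinue with RNA at or above 50 c/mL, but only when the reason is not an adverse event.

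**The concern.** A site that withholds an injection for toxicity finds two instructions, each justified as limiting resistance: one to hold all antiretrovirals, the other to start a different active regimen. Section 6.9.1 itself describes participants on the long-acting drugs as being at risk of resistance if ART is interrupted. Which passage is followed bears on participant safety.

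It may also bear on the primary endpoint. If other ART is started, the Snapshot outcome turns on whether that counts as a permitted change, and the protocol gives support to both answers. Clinically similar participants could then be classified differently, within an arm or between arms.

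**Working it through.** **1. Does scope separate the rules?** Section 6.9 sits above both dosing routes and names neither. Section 7.4.4.1 gives a restart time for oral dosing, then turns to intramuscular dosing and refers to 6.9.1. Section 6.9.1 applies to any intramuscular interruption and has no exception for toxicity. Section 5.5.5.2, by contrast, carries a note that its interruption guidance may not apply to participants on long-acting treatment; 6.9 and 7.4.4.1 carry no such note. A toxicity hold of an injection therefore falls under both rules.

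**2. Do other provisions settle it?** Oral bridging (6.8.1) is for pre-planned missed visits and uses oral CAB and RPV, the same two agents, so it is not alternative ART. The follow-up HAART in 4.2.4 and 6.10 is for participants who discontinue, not for a temporary hold with restart.

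**3. How would a participant given other ART be scored at Week 48?**

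| Reading | Basis | Primary endpoint (9.3.1) |
|---|---|---|
| ART is permitted; injections resume | 6.9.1 directs it | Scored on the RNA measured on treatment in the window |
| ART is a non-permitted change before the window, no evaluable data | 5.5.5, 6.13.2 | RNA at or above 50 c/mL: primary failure |
| ART is a substitution; treatment stops, reason recorded as adverse event | 5.5 | Not a failure under the discontinuation limb |

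The text supports each row and does not choose among them.

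**4. The plan's own figures.** Inputs from Section 9.1: 510 per arm, true failure rates 3% (Q8W) and 2% (Q4W), margin 4%, one-sided 2.5%, unpooled Z.

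- SE = sqrt(0.03×0.97/510 + 0.02×0.98/510) = 0.00977.
- Power = Φ((0.04 − 0.01)/0.00977 − 1.96) = 86.7%, which agrees with the stated value of at least 85%.
- The largest passing observed difference with Q4W at 2% computes to 1.92 points, as stated.

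**5. Sensitivity only.** One participant is 1/510 = 0.196 points. Expected events are about 15 v 10. The upper limit is d + 1.96×sqrt(p8(1−p8)/510 + p4(1−p4)/510), a simple stand-in for the stratified interval in 9.3.1.

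- 15 v 10 gives 2.88%; 20 v 10 gives 4.03%.

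With extra Snapshot failures at assumed rates, not taken from the protocol:

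| Added failures | Result |
|---|---|
| 0.5 or 1 point in both arms | Power about 80% or 74% |
| 0.5 or 1 point in Q8W only | Power about 69% or 47% |
| 0.5 or 1 point in Q4W only, true rates 6% v 2% | Chance of wrongly declaring non-inferiority rises from 2.5% to about 6% or 12% |

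The direction depends entirely on which arm is assumed to carry the cases.

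**The case against.** The strongest reply is that the rules address successive steps. On study the participant's only antiretrovirals are CAB and RPV, so holding all of them means not holding one while continuing the other; Section 6.9.1 then says what should cover the decline in drug levels. Section 7.4.4.1 refers to 6.9.1 for intramuscular interruptions outside the dosing window, and 6.9 requires every interruption decision to be discussed with the Medical Monitor in advance. Section 5.5 can also be read as a pathway: a participant who needs other ART stops study treatment and enters long-term follow-up.

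This reading is plausible, but it is not what the text says. Sections 6.9 and 7.4.4.1 speak of all antiretroviral or ART medications and do not limit this to the study regimen. Consultation limits divergence between sites but supplies no common rule. The pathway reading also leaves unexplained how a temporary hold under 7.4.4.3 would combine with alternative ART.

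The objection does stand against two stronger inferences:

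- **That the participant is either left without ART or becomes a primary failure.** Section 6.9.1 notes that both long-acting drugs may be measurable for more than a year, so holding everything means that no ART is being given, not that no drug is present. A toxicity hold ending in an adverse-event discontinuation is not scored as failure by the discontinuation limb of 9.3.1.
- **That five cases would turn a pass into a fail.** The arithmetic is right (20 v 10 gives 4.03%), but it puts every case in Q8W and largely restates the tipping point in Section 9.1. Nothing in the protocol supports that direction. In LATTE-2 (Section 2.2), adverse events leading to withdrawal through Week 96 were 2% on Q8W and 7% on Q4W; these are withdrawals rather than holds, but they lean the other way.

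**Conclusion.** The conflict between Sections 6.9 and 7.4.4.1 on one side and 6.9.1 on the other is real for an injection held for toxicity. It concerns whether a participant receives ART, so it is more than missing detail. Which rule is clinically right is not a matter for this review.

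The endpoint consequence is narrower. Whether ART started under 6.9.1 is permitted per protocol has no single answer, so its Snapshot classification is ambiguous. Scoring as a primary failure arises only if that ART is treated as a non-permitted change. With no rate of toxicity holds and no split by arm in the protocol, the effect on the result cannot be quantified. The sensitivity figures show only that a handful of cases handled differently could matter, in either direction. The detailed Snapshot derivation is properly left to the analysis plan, but whether a treatment change is permitted is a protocol question that the analysis plan would need answered.

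**What to change.** 1. Reconcile Sections 6.9, 6.9.1 and 7.4.4.1 into one consistent instruction for held injections, distinct from held oral dosing, and state whether the rule on holding all medications covers only the two study drugs. The clinical team decides the content.
2. Align Sections 5.5, 5.5.5 and 6.13.2 with that instruction.
3. State once whether ART started under it counts as permitted per protocol for Section 9.3.1, so that such participants are classified the same way in both arms.

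The cost is amendment wording and one sentence on classification, with no added participants or procedures.
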